**End-of-study visit at six months**

- Date of visit;
- Patient's clinical data. Urinary symptoms (USP score). Concomitant bladder treatments
- Self-catheterisation: methods of use, continuation of self-catheterisation, information on stopping, if applicable
- Catheter chosen: continue self-catheterisation with the chosen catheter or catheter change, information on the catheter change, if applicable
- Patient questionnaire on catheter use and satisfaction (on a five point scale)
- IC-Di-Q
- I-CAS
- Possible adverse events

**9 STATISTICS****9.1 Number of subjects needed**

The primary objective of this study is to assess, with sufficient precision, the final criteria for choosing SpeediCath catheters.

In this context, the number of patients required depends on the desired precision for the frequencies observed of the choice criteria and the alpha risk. The table below shows that the precision obtained (95% confidence interval) for the percentages observed between 5% and 50% (or 95%-50% for the additional percentage) with 250 patients will be from  $\pm 2.75\%$  to  $6.25\%$  ( $\pm 2.75\%$  for the percentages close to 95% or 5% and  $\pm 6.25\%$  for percentages close to 50%).

**Number of patients required according to the desired precision (95% confidence interval) for an observed percentage (normal approximation).**

Precision	Percent observed									
	5% / 95%	10% / 90%	15% / 85%	20% / 80%	25% / 75%	30% / 70%	35% / 65%	40% / 60%	45% / 55%	50% / 50%
$\pm 2.5\%$	292	553	784	983	1152	1291	1398	1475	1521	1537
$\pm 2.75\%$	241	457	648	813	952	1067	1156	1219	1257	1270
$\pm 3.0\%$	203	384	544	683	800	896	971	1024	1056	1067
$\pm 3.75\%$	130	246	348	437	512	574	621	656	676	683
$\pm 4.0\%$	114	216	306	384	450	504	546	576	594	600
$\pm 4.5\%$	90	171	242	304	356	398	432	455	470	474
$\pm 5.0\%$	73	138	196	246	288	323	350	369	380	384
$\pm 5.5\%$	60	114	162	203	238	267	289	305	314	317
$\pm 6.0\%$	51	96	136	171	200	224	243	256	264	267
$\pm 6.25\%$	47	88	125	157	184	206	224	236	243	246
$\pm 6.5\%$	43	82	116	145	170	191	207	218	225	227

In summary, 250 patients will be needed in this study to allow for an assessment with sufficient accuracy ( $\pm 2.75\%$  to  $\pm 6.25\%$ ) of the final choice criteria for SC catheters.

And if we do not recover the final choice criteria of 10% of the enrolled patients (patients lost to follow-up, withdrawal of consent during the study, etc.), we will nevertheless have a precision ranging from  $\pm 3.0\%$  to  $\pm 6.5\%$  of the observed percentages.

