- ✓ The difficulties experienced by patients during the ISC will be measured by the Intermittent Catheterisation Difficulty Questionnaire IC-Di-Q. This is a patient questionnaire validated in French, and aims to assess the difficulties encountered during the performance of the ISC. It explores in thirteen questions many factors such as pain, blockage, bleeding, spasticity, urethral sphincter spasm, in terms of frequency of occurrence and intensity. The purpose of this questionnaire is to identify the challenges faced by patients, and to follow up their progress after alternatives or solutions have been put in place (including adapting to the type of catheter).
- ✓ Patient adherence or compliance to the ISC will be measured by the Intermittent Catheterisation Adherence Scale (I-CAS). This is a patient questionnaire validated in French consisting of eight questions, seven of which have a binary answer (yes/no) and one has five proposed responses. The score ranges from 0 for strong ISC adhesion to 8 for very low adhesion.

- ✓ A study-specific self-questionnaire was also created with the support of the scientific council to determine the reasons for the patient's choice of the catheter. This questionnaire includes the patient's independent criteria (e.g. nurse's advice) and patient-specific criteria (e.g. ease of use, discretion).

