## 7 STUDY IMPLEMENTATION

### 7.1 Inclusion

The study is for people who are newly educated in ISC and who have chosen to use a catheter from the SpeediCath range after they have completed their self-catheterisation training. It will be conducted with approximately fifty investigator sites. To ensure good representativeness, the number of patients/sites will be limited to five.

In order to limit selection bias, investigators should propose, if possible, study participation to all eligible patients who are seen consecutively. Screened eligible patients will have been informed of the study and will have wanted to participate in it (non-opposition).

After verification of the screening criteria, informing the patient will be carried out. At the end of this step, and in the absence of patient opposition, a patient identification number will be assigned to him/her and will be used throughout the study.

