#### Number of investigator sites and maximum number of patients per site.

Depending on the recruitment capacity of the investigator sites and the expected duration of the recruitment period, four to five patients will be enrolled per site with a maximum of twelve patients per investigator. As a result, a total of fifty active investigator sites will achieve the target of the 250 expected patients.

At the start of the study, forty investigator sites will be set up. If necessary, ten additional sites will then be added. Investigator sites will be selected to ensure representativeness in the treated patient population.

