## 9.2 Statistical analysis

The analyses will be performed using the SAS V9.4 software (or earlier version), on a frozen database, after review of data allowing to identify protocol deviations and their potential impact on the analysis criteria. Protocol deviations will be classified as minor or major. Major deviations will lead to the exclusion of patients from the per protocol (PP) population. The distribution of patients in the analysis populations will be reviewed and approved by the sponsor before the database freeze.

The description of all the parameters will be based on the type of catheter and according to the gender of the patients. Quantitative parameters will be described using the following statistics: number of non-missing data, mean, standard deviation, median, first and third quartile, minimum and maximum. Qualitative parameters will be described using the headcounts and the percentages. These will be calculated from the number of non-missing observations. In all cases, the number of missing data will be specified.

Univariate analyses then multivariate analyses by logistic regressions will be performed to identify, among the data studied (patient choice criteria at V1, his/her final choice at V3, his/her adherence to ISC, his/her satisfaction with the catheter, his/her challenges during ISC, his/her clinical and socio-demographic characteristics, etc.), the predictive factors of the final choice of the SpeediCath catheter (Standard, Compact or Flex for male patients; Standard, Compact or Compact Eve for female patients).

The same will be done for adherence to ISC at V3 (with clinical and socio-demographic characteristics at V1, I-CAT score at V1, ICDQ score at V2, type of catheter chosen).

The other secondary endpoints will be described at the different time points and according to the catheter type.

Missing data at the time of analysis will not be replaced and will be considered as such.

A statistical analysis plan will be written after approval of the protocol. This document will have a reference value for the statistical analyses.

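### The ±2.75% to ±6.25% precision in section 9.1 assumes 250 independent patients, although patients come in groups of four to five per site and site staff influence the choice being measured

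*Protocol*

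**What the plan says.** Protocol section 9.1 sizes the study on precision alone. It says that "the number of patients required depends on the desired precision for the frequencies observed of the choice criteria and the alpha risk" and names no other driver. The table is titled "Number of patients required according to the desired precision (95% confidence interval) for an observed percentage (normal approximation". From it the protocol reads ±2.75% (percentages near 5% or 95%) to ±6.25% (near 50%) for 250 patients, and it concludes that "250 patients will be needed in this study to allow for an assessment with sufficient accuracy". It then considers the case "if we do not recover the final choice criteria of 10% of the enrolled patients" and gives ±3.0% to ±6.5%.

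On sites, the second part of 9.1 plans that "four to five patients will be enrolled per site with a maximum of twelve patients per investigator", with fifty active sites to reach 250: forty at the start and ten more if needed. Section 7.1 says that "the number of patients/sites will be limited to five".

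On how the choice comes about:
- Section 3 says that training is given mainly by nurses or a specialist doctor.
- Section 8 records which catheters the nurse showed the patient.
- Section 3 says of the study's own choice questionnaire: "This questionnaire includes the patient's independent criteria (e.g. nurse's advice", alongside patient-specific criteria such as ease of use.

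Section 9.2 describes categorical data by counts and percentages and says that "Univariate analyses then multivariate analyses by logistic regressions will be performed". It does not mention site, and it leaves the detail to a statistical analysis plan (SAP).

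**The concern.** Patients at one site share the staff who train them, the range of catheters shown and the advice given. Section 6.2.1 requires only that at least two types were introduced, so the range shown can differ between sites. Some of the criteria counted in the primary objective, the nurse's advice above all, are therefore likely to be more alike within a site than between sites. When answers are positively correlated within sites, 250 patients carry less information than 250 independent ones, and a formula for one proportion under simple random sampling understates the uncertainty.

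The precision is the only quantitative support for 250 patients. Section 4 wants the results to guide counselling of individual patients, so a criterion that partly reflects local habit should not be reported with more certainty than the design gives.

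**Working it through.** **Inputs from the protocol.** n = 250; 10% loss, so n = 225; two-sided 95%, normal approximation (9.1); fifty sites with four to five patients each (9.1). **Assumed, because the protocol gives no figure:** an ICC of 0.02 to 0.10, the same for every criterion.

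**Step 1: reproduce the stated figures.** Half-width = 1.96 × √(p(1−p)/n).
- n = 250, p = 50%: 1.96 × √(0.25/250) = 6.20% (stated ±6.25%).
- n = 250, p = 5%: 1.96 × √(0.0475/250) = 2.70% (stated ±2.75%).
- n = 225: 6.53% at 50% (stated ±6.5%) and 2.85% at 5% (stated ±3.0%).

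The inverse formula, n = 1.96² p(1−p)/d², reproduces all 110 cells of the table to within rounding. The table is therefore correct under independence, and independence is what it assumes.

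**Step 2: add the design effect.** DE = 1 + (m − 1) × ICC, where m is the number of patients per site. Half-width = 1.96 × √(p(1−p) × DE/n). A nominal 95% interval that ignores site covers 2Φ(1.96/√DE) − 1. With m = 5 and n = 250:

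| ICC (assumed) | DE | Effective n | Half-width at 5% | Half-width at 50% | Coverage if site is ignored |
|---|---|---|---|---|---|
| 0 | 1.00 | 250 | ±2.70% | ±6.20% | 95.0% |
| 0.02 | 1.08 | 231 | ±2.81% | ±6.44% | 94.1% |
| 0.05 | 1.20 | 208 | ±2.96% | ±6.79% | 92.6% |
| 0.10 | 1.40 | 179 | ±3.20% | ±7.33% | 90.2% |

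With m = 4, the half-width at 50% is ±6.38%, ±6.65% and ±7.07% at ICC 0.02, 0.05 and 0.10.

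**Step 3: the same with 10% loss.** n = 225 over fifty sites is 4.5 per site. DE is 1.07, 1.175 and 1.35 at ICC 0.02, 0.05 and 0.10. The half-width at 50% is ±6.76%, ±7.08% and ±7.59%, against the stated ±6.5%.

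**Step 4: slack in the stated figure.** With five per site, ±6.25% at 50% is exceeded once ICC passes ((6.25/6.198)² − 1)/4 ≈ 0.004. At 5%, ±2.75% is exceeded once ICC passes ((2.75/2.702)² − 1)/4 ≈ 0.009. This shows only that the stated bounds have almost no reserve. It does not show that the loss is large.

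**Step 5: why the cap matters.** Forty sites capped at five give at most 40 × 5 = 200 patients, and fifty reach 250 only if every site fills its five. If forty sites supplied all 250, for example thirty with six and ten with seven, the weighted site size would be (30×36 + 10×49)/250 = 6.28. The half-width at 50% would be ±6.97% at ICC 0.05 and ±7.66% at ICC 0.10.

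**The case against.** The strongest reply is that the effect is modest and rests on an assumed ICC. The primary criteria are collected at V3, after six months of use, and they include patient-specific items on which the site may have little influence. Every patient has been shown at least two types. At ICC 0.02 with five per site, ±6.44% is still inside the ±6.5% that the protocol accepts after losses. The study is exploratory, with no hypothesis test and no precision threshold, and many small sites already keep the design effect low. All of this stands and limits the weight of the point. It does not remove it, because 9.1 itself fixes the figure and leaves the assumption unstated.

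Three stronger readings are tempting, and the protocol does not support them.

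- **A reader might infer that the regressions in 9.2 assume independent patients.** Section 9.2 neither includes nor excludes site, and it defers to a SAP. Ignoring site also does not shorten every standard error in a regression; that depends on whether the covariate varies between or within sites.
- **A reader might infer clusters of twelve.** The sentence sets twelve per investigator, although its subheading speaks of patients per site, and 7.1 caps sites at five. Twelve at every site would mean about 250/12 ≈ 21 sites, not fifty.
- **A reader might infer that the primary result is a set of intervals that are too short.** Section 9.2 specifies counts and percentages and names no interval. The coverage figures apply to 95% intervals computed in the manner of 9.1, if such intervals are reported.

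**Conclusion.** The point holds for the precision statement in 9.1. The stated half-widths are arithmetically right for independent patients and optimistic under any positive within-site correlation, which the way catheters are presented and chosen makes plausible. With five patients per site and ICC 0.02 to 0.10, the half-width at 50% is about ±6.4% to ±7.3% instead of ±6.25%, and at 5% about ±2.8% to ±3.2% instead of ±2.75%. Intervals that ignore site would cover about 94% to 90%. With 10% loss and ICC 0.05 to 0.10, the half-width at 50% is about ±7.1% to ±7.6% instead of ±6.5%.

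These sizes rest on an assumed ICC, common to all criteria, and on nearly equal sites. At ICC 0.02 or below the loss is small. Criteria that depend on staff may lie higher in the range than those that depend on the patient's own experience. The change is worth making because it is cheap. The sample size need not be reopened, and no error in the regressions has been shown.

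**What to change.** 1. **Section 9.1.** State that ±2.75% to ±6.25%, and ±3.0% to ±6.5% after losses, assume no correlation within sites. Add the range with it: with five per site and an assumed ICC of 0.02 to 0.10, about ±2.8% to ±3.2% at 5% and ±6.4% to ±7.3% at 50%. After 10% loss, give about ±7.1% to ±7.6% at 50% for ICC 0.05 to 0.10.
2. **Primary percentages.** Specify that 95% intervals for the final choice criteria are computed with site as the cluster, for example with SAS SURVEYFREQ.
3. **Sections 7.1 and 9.1.** Reconcile the cap of five per site with the maximum of twelve per investigator, and say whether investigator and site mean the same unit. The cap sets the design effect.
4. **For the SAP, as a recommendation.** Say how site is handled in the logistic regressions, for example by site-clustered standard errors. If the models are fitted separately for men and women, an even split would leave about 2.5 patients per site. A site random effect may then be unstable.

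The cost is a few sentences, a standard SAS procedure and a slightly less favourable stated precision. No further patients or data are needed.

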#### Number of investigator sites and maximum number of patients per site.

Depending on the recruitment capacity of the investigator sites and the expected duration of the recruitment period, four to five patients will be enrolled per site with a maximum of twelve patients per investigator. As a result, a total of fifty active investigator sites will achieve the target of the 250 expected patients.

At the start of the study, forty investigator sites will be set up. If necessary, ten additional sites will then be added. Investigator sites will be selected to ensure representativeness in the treated patient population.

## 9.2 Statistical analysis

The analyses will be performed using the SAS V9.4 software (or earlier version), on a frozen database, after review of data allowing to identify protocol deviations and their potential impact on the analysis criteria. Protocol deviations will be classified as minor or major. Major deviations will lead to the exclusion of patients from the per protocol (PP) population. The distribution of patients in the analysis populations will be reviewed and approved by the sponsor before the database freeze.

The description of all the parameters will be based on the type of catheter and according to the gender of the patients. Quantitative parameters will be described using the following statistics: number of non-missing data, mean, standard deviation, median, first and third quartile, minimum and maximum. Qualitative parameters will be described using the headcounts and the percentages. These will be calculated from the number of non-missing observations. In all cases, the number of missing data will be specified.

Univariate analyses then multivariate analyses by logistic regressions will be performed to identify, among the data studied (patient choice criteria at V1, his/her final choice at V3, his/her adherence to ISC, his/her satisfaction with the catheter, his/her challenges during ISC, his/her clinical and socio-demographic characteristics, etc.), the predictive factors of the final choice of the SpeediCath catheter (Standard, Compact or Flex for male patients; Standard, Compact or Compact Eve for female patients).

The same will be done for adherence to ISC at V3 (with clinical and socio-demographic characteristics at V1, I-CAT score at V1, ICDQ score at V2, type of catheter chosen).

The other secondary endpoints will be described at the different time points and according to the catheter type.

Missing data at the time of analysis will not be replaced and will be considered as such.

A statistical analysis plan will be written after approval of the protocol. This document will have a reference value for the statistical analyses.

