2 STUDY FLOWCHART

V1 - Screening Visit – Inclusion D0		
	Investigator	Patient information
		Inclusion and non-inclusion criteria
		Socio-demographic data
		Clinical data and scores
		Acceptance of the ISC (I-CAT)
		Concomitant bladder treatments
		Method for choosing the catheter and the patient's criteria for choosing the catheter
		Education conditions and ISC methods
		Adverse events
V2 - Follow-up visit - 3 to 12 weeks		
	Investigator	Clinical data
		Continuation of ISC
		Continued use of chosen catheter
		Concomitant bladder treatments
		Adverse events
	Patient	Daily frequency of the ISC
		Overall impression with the ISC
		Satisfaction with the catheter (on a five point scale)
		Challenges during the ISC (IC-Di-Q)
		ISC adherence (I-CAS)
V3 - End of study visit – around 6 months		
	Investigator	Clinical data
		Continuation of ISC
		Continued use of chosen catheter.
		Concomitant bladder treatments
		Adverse events
	Patient	Daily frequency of the ISC
		Overall impression with the ISC
		Satisfaction with the catheter (on a five point scale)
		Patient's final choice criteria for the catheter
		Challenges during the ISC (IC-Di-Q)
		ISC adherence (I-CAS)

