## 4 STUDY OBJECTIVES

The purpose of this exploratory study is to determine the major criteria in the choice of catheter by patients.

The results will allow for personalised counselling to be put in place for each patient, in order to offer him/her as a first-line treatment the catheter that is the most appropriate for his/her profile, with the goal of facilitating ISC learning and improving ISC adherence and acceptance.

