### 4.2 Secondary objectives

The secondary objectives are as follows:

- Document the criteria for the patient's initial choice of the SC catheter: determined by self-questionnaire at V1
- Document patient satisfaction with the SC catheter: measured on a five point scale at V2 and V3
- Document the challenges encountered during the first six months of the ISC: measured by the IC-Di-Q at V2 and V3
- Determine patient adherence to the ISC over the first six months: measured by I-CAS at V2 and V3.
- Determine the variables associated with the catheter selection and adherence to the ISC.

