### 7.2 Participation in the study

The subject's participation in the study does not involve any additional examinations compared to the usual management of a patient. The study will be offered to subjects until the threshold headcount is reached at each site or until the total headcount is reached.

Since the study is observational, patients are free to make the decision to change catheters during follow-up if the initially chosen catheter is not suitable for them. In this case, this change will be documented as well as the model and brand of the new catheter chosen and the patient will continue the study normally.

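### The model for predictors of the final catheter type admits the final choice itself, and scores that arise only after a catheter is in use

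*Protocol*

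**What the plan says.** Protocol section 9.2 describes univariate and then multivariate logistic regressions to identify "the predictive factors of the final choice of the SpeediCath catheter", separately defined for men (Standard, Compact or Flex) and women (Standard, Compact or Compact Eve). The candidates are "patient choice criteria at V1, his/her final choice at V3, his/her adherence to ISC, his/her satisfaction with the catheter, his/her challenges during ISC", followed by clinical and socio-demographic characteristics and an open-ended etcetera.

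The next paragraph of 9.2 plans a model of adherence at V3. There the predictors are listed "with clinical and socio-demographic characteristics at V1, I-CAT score at V1, ICDQ score at V2, type of catheter chosen", so the timing of most of them is fixed.

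The timing of the measurements is set elsewhere in the protocol:

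- Section 4.2: "Document patient satisfaction with the SC catheter: measured on a five point scale at V2 and V3" and "Determine patient adherence to the ISC over the first six months: measured by I-CAS at V2 and V3". The difficulty questionnaire is likewise assigned to V2 and V3.
- Section 2 (flowchart), V3 only: "Patient's final choice criteria for the catheter".
- Section 8: the first SpeediCath catheter and the reasons for it are recorded at inclusion. The adherence, satisfaction and difficulty scores are not.
- Section 7.2: "patients are free to make the decision to change catheters during follow-up", and those who change remain in the study.

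**The concern.** A predictive factor has to exist before the thing it predicts. Several of the named candidates do not, and for others the text leaves open whether they do. The protocol also runs the relation both ways: adherence is a candidate predictor of catheter type in the first model, and catheter type is a predictor of adherence in the second.

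This matters because of the intended use. Section 4 says the results should make it possible to "offer him/her as a first-line treatment the catheter that is the most appropriate for his/her profile". When self-catheterisation starts, only V1 information is available. A model containing V2 or V3 scores cannot be applied then. It may also present what a catheter does to its users as a reason for choosing it, and it can distort the odds ratios of the V1 characteristics that could inform advice.

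**Working it through.** **The plan's own figures.** The only sizing figures concern precision, and they reproduce: n = 1.96² × p(1−p)/d² gives 241 for p = 5%, d = 2.75%, and 246 for p = 50%, d = 6.25%, as in section 9.1. The concern does not depend on them. From 9.1 the check takes only the 250 patients and the 10% without final choice data: 250 × 0.9 = 225.

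**Step 1: timing of each candidate against the outcome (final catheter type at V3).**

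| Candidate in 9.2 | Collected | Relation to the final choice |
|---|---|---|
| Choice criteria at V1 | V1 | Precede it |
| Clinical and socio-demographic data | Socio-demographic at V1; clinical at V1, V2 and V3 | V1 values precede it |
| Final choice at V3, read literally | V3 | Is the outcome |
| Final choice at V3, read as the criteria for it | V3 | Concurrent |
| Adherence, satisfaction, difficulties at V2 | V2 | Precede it only for patients who change catheter after V2 |
| Adherence, satisfaction, difficulties at V3 | V3 | At best concurrent |

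For a patient who keeps the V1 catheter, even a V2 score is obtained while using the catheter already chosen. Fixing the visit at V2 reduces the problem but does not remove it.

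**Step 2: how often would a pure consequence be flagged?** The protocol gives none of the effect sizes or splits below; they are assumptions. With an equal split by sex and three types per sex, 225/2/3 = 37.5, taken as 37 per type. With only two types used per sex, 225/2/2 = 56. Satisfaction is dichotomised, is 65% in the reference type, and differs between two types solely because of the type. At 80% v 65% its odds ratio is (0.80/0.20)/(0.65/0.35) = 2.15. Exact enumeration of two binomials with Pearson's chi-square at 5% gives:

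| Satisfaction | 37 per type | 56 per type |
|---|---|---|
| 75% v 65% | 16% | 21% |
| 80% v 65% | 31% | 43% |
| 90% v 65% | 76% | 91% |

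A separate simulation used a different set-up: 225 patients, two types allocated at random, a continuous V3 score shifted by the catheter, 2,000 runs. Shifts of 0, 0.3 and 0.5 SD gave p<0.05 in 5.5%, 60% and 96% of runs, with median odds ratios of 1.00, 1.35 and 1.65. Nothing predicted the choice in that simulation.

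**Step 3: what happens to a true V1 factor?** Let T be type, X a V1 factor and S satisfaction. Assume T is split 50/50, X has prevalence 50%, S is 65% in the reference type, the T–S odds ratio is 2.154, and X also affects S. With S in the model, the odds ratio of X for T becomes

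OR_adj = OR × [P(S=0|T=1,X=1) × P(S=0|T=0,X=0)] / [P(S=0|T=0,X=1) × P(S=0|T=1,X=0)].

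Example: X truly unrelated to T (OR = 1) and an X–S odds ratio of 2. An average satisfaction of 65% in the reference type requires satisfaction odds of 1.337 at X=0 and 2.674 at X=1. Multiplying by 2.154 gives 2.880 and 5.760 in the other type. The probabilities of not being satisfied are 0.4279 and 0.2721 (reference type, X=0 and X=1) and 0.2577 and 0.1479 (other type). So OR_adj = (0.1479 × 0.4279)/(0.2721 × 0.2577) = 0.90.

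| X–S odds ratio | True OR 2.0 becomes | True OR 1.0 becomes |
|---|---|---|
| 1.5 | 1.88 | 0.94 |
| 2 | 1.81 | 0.90 |
| 3 | 1.72 | 0.85 |

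**The case against.** The visit of each covariate is commonly settled in the SAP. The protocol announces one, and the open-ended candidate list reads as a pool rather than a model specification. The reference to the final choice is probably shorthand for the final choice criteria, and relating stated reasons to the catheter chosen is close to the study's purpose. The secondary objective speaks of associated variables, and for associations it is no contradiction that type is the outcome in one model and a covariate in the other. Patients who keep their catheter may be deciding again in the light of experience. The flag rates above are simply power to detect a real association between type and satisfaction. The odds-ratio shifts are small beside sampling error: with 37 per type and a true odds ratio of 2.0, the standard error of the log odds ratio is about 0.47, so the 95% interval runs from about 0.8 to 5.0.

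Part of this stands. The shifts are modest, the analysis is exploratory, and the shorthand reading is plausible. The rest does not rescue the text. On the shorthand reading the item is still recorded with the outcome. An SAP can choose V2 or V3, but for patients who keep the V1 catheter both visits follow the choice, so an SAP faithful to 9.2 inherits the defect. The protocol fixed visits for the adherence model, so timing was not simply being left for later. The association between type and satisfaction may well be real; the error is calling satisfaction a predictor of type. Reconsideration in the light of experience can be studied properly as catheter change after V2.

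**Conclusion.** The concern holds, with high confidence, from the protocol's own text. As written, section 9.2 admits the outcome or a same-visit item, together with scores generated by catheter use, as candidate predictive factors of catheter type. The conclusion rests on the visit schedule and needs no numerical assumption. The size does: under the assumed splits and effects, a pure consequence of the catheter is flagged in 16% to 91% of studies (31% in the central case), and a V1 odds ratio of 2.0 shrinks to between 1.72 and 1.88. The main harm is the direction of inference rather than the numerical bias. It should be fixed, but it is confined to a secondary exploratory objective. The descriptive primary objective and the sample size are unaffected. The SAP was not available and may already narrow the candidate list.

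**What to change.** In section 9.2, and correspondingly in the SAP:

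1. Remove the V3 final choice from the candidate list. If the criteria for that choice were meant, say so and describe them by catheter type without entering them as predictors.
2. Restrict the predictive model of final type to V1 data: choice criteria, socio-demographic and clinical characteristics, I-CAT score and training conditions. Adjustment for which catheters were presented at V1 is optional; section 8 already collects this.
3. Use V2 satisfaction, adherence and difficulty scores as predictors only in a separate analysis of catheter change after V2, where they do come first.
4. Report V2 and V3 satisfaction, adherence and difficulties as outcomes by catheter type. This keeps the study's interest in which choice gives satisfaction.

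The cost is rewording; all the data are already collected. The V1-only model may explain less variation, and the analysis of later change may rest on few patients.
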